12.2.4.1. Primary analysis

The primary efficacy endpoint, change from baseline at Week 104 in ADAS-Cog₁₃ total score, will be analyzed using an MMRM model that includes the fixed effects of treatment, visit (categorical covariate), treatment-by-visit interaction, disease status at baseline (MCI due to AD or mild AD), APOE4 status (carrier versus non-carrier), baseline ADAS-Cog₁₃ total score (continuous covariate), concomitant AChEI use at baseline (yes/no), age at baseline, country, and baseline ADAS-Cog₁₃ total score-by-visit interaction. An unstructured variance-covariance matrix will be used.

For each of the 2 AZD3293 treatment groups, the null hypothesis is that the change from baseline in ADAS-Cog₁₃ total score at Week 104 is equal to the change from baseline in ADASCog₁₃ total score at Week 104 for the placebo treatment group. The alternative hypothesis is that the change from baseline in ADAS-Cog₁₃ total score at Week 104 for an AZD3293 treatment group ($\mu_{AZD3293}$) is not equal to the change from baseline in ADAS-Cog₁₃ total score at Week 104 for the placebo treatment group ($\mu_{Placebo}$). These hypotheses can be represented as follows:

 H_{Null} : $\mu_{\text{AZD3293}} = \mu_{\text{Placebo}}$

 $H_{Alternative}$: $\mu_{AZD3293} \neq \mu_{Placebo}$

The primary analysis will evaluate whether there is a difference between treatment groups in the mean change from baseline in ADAS-Cog₁₃ total score at Week 104 and will be based on the treatment difference at Week 104 using least-squares means. This will be accomplished by using appropriate linear contrasts of the parameters in the model described above.

As a sensitivity analysis, a method for missing value imputation based on pattern mixture models will be implemented. It is assumed that after discontinuation from the study, patients receiving the AZD3293 doses will exhibit the same future evolution of the disease as patients on placebo treatment. This method uses sequential regression and multiple imputation methodology to impute missing values for visits after a patient's discontinuation from the study. Based on the available data from placebo-treated patients, the missing values from the placebo and AZD3293 treatment groups will be imputed sequentially using a procedure for monotone missing data patterns until all visits are imputed.

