5.2.2. Procedures for randomization

Patient eligibility will be established before randomized treatment assignment (see Section 4 for inclusion and exclusion criteria). The randomization will be stratified for disease status at baseline (MCI due to AD or mild AD).

The stratified randomization schedule will be prepared by the CCl Biostatistics

Department on behalf of the sponsor. Randomization codes will be allocated in blocks within strata to AZD3293 20 mg, AZD3293 50 mg, or placebo in a ratio of 1:1:1, stratified by MCI due to AD and mild AD dementia. Enrollment rates in MCI due to AD and mild AD strata will be monitored.

If a patient withdraws from the study, the patient's study identifier and randomization code will not be reused, and the patient will not be allowed to re-enter the study.

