12.3. Determination of sample size

12.3.1. Efficacy

The sample size for this study, 734 randomized patients in each of 3 treatment groups, was selected to be consistent with the hypothesis described in Section 1.2. The sample-size calculations are based on the primary efficacy endpoint, change from baseline in ADAS-Cog₁₃ total score at Week 104.

Assumptions about minimally clinically significant differences as measured by the ADAS-Cog total score were based on 18 month solanezumab results extrapolated to 24 months. In this database, the least-squares treatment difference from placebo in mean change in ADAS-Cog total score from baseline at 80 weeks in the mild AD population of APOE4 carriers with CDR global score = 0.5 was 1.68 units with a standard deviation (SD) of 9.72. A linear extrapolation using these results coupled with results at 28 and 52 weeks resulted in 104 week estimates of 2.24 (12.96). Using these estimates to approximate an MCI population, this expected difference translates into an effect size of 0.17.

Compared with the MCI population, deterioration of cognition in patients with mild AD has been observed to be somewhat faster. The least-squares treatment difference from placebo in mean change in ADAS-Cog total score from baseline at 80 weeks in the solanezumab mild AD population (enriched by restricting to APOE4 carriers) was 2.87 (10.16) units. A linear extrapolation using these results coupled with results at 28 and 52 weeks resulted in 104 week estimates of 3.83 (13.54). This expected difference translates into an effect size of 0.28.

Similar calculations were made for the key secondary endpoint ADCS-iADL. The least-squares mean change in ADCS-iADL score from baseline at 80 weeks in the mild placebo-treated population of APOE4 carriers with CDR global score = 0.5 was 0.31 (8.39) units. A linear extrapolation using these results coupled with results at 28 and 52 weeks resulted in 104 week estimates of 0.41 (11.19). Using these estimates to approximate an MCI population, this expected difference translates into an effect size of 0.04. The least-squares mean change in ADCS iADL score from baseline at 80 weeks in the mild AD population (enriched by restricting to APOE4 carriers) was 2.14 (9.81) units. A linear extrapolation using these results coupled with results at 28 and 52 weeks resulted in 104 week estimates of 2.85 (13.08). This expected difference translates into an effect size of 0.22.

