The study will enroll a total of 2202 patients (734 patients per group). Assuming α =0.025 and the effect size among the patients who discontinue without completing the study is 50% of the effect size of the completers, the power for the mixture of MCI and mild AD patients for a single dose is 96% for ADAS-Cog (adjusted effect size is 0.21); for iADL it is 60% (adjusted effect size is 0.13). The power to show statistical significance for the mild AD subpopulation is 93% (adjusted effect size is 0.24) and 75% (adjusted effect size is 0.19) for ADAS-Cog and iADL, respectively. The power to show statistical significance for the MCI subpopulation is 26% (adjusted effect size is 0.14) and 3% (adjusted effect size is 0.03) for ADAS-Cog and iADL, respectively (Table 7).

Population	ADAS-Cog ES per Dose	ADAS-Cog Power per Dose	ADCS-iADL ES per Dose	ADCS-iADL Power per Dose
Overall*	0.21	96%	0.13	60%
Mild AD	0.24	93%	0.19	75%
MCI	0.14	26%	0.03	3%

Table 7. Effect Size and Power per Dose for Mild AD and MCI Patient Populations

Abbreviations: AD Alzheimer's Disease; ADAS-Cog Alzheimer's Disease Assessment Scale-Cognition; ADCS-iADL The Alzheimer's Disease Cooperative Study Activities of Daily Living Inventory - instrumental items score; ES Effect size; MCI Mild cognitive impairment.

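### The primary MMRM gives disease status no visit interaction although mild AD is said to decline faster than MCI; the Week 104 standard error comes out slightly conservative, and one added term corrects it

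*Protocol*

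**What the plan says.** - **Model.** Protocol Section 12.2.4.1 (and the synopsis) gives the term list for change from baseline in ADAS-Cog13. It contains "treatment-by-visit interaction, disease status at baseline (MCI due to AD or mild AD), APOE4 status (carrier versus non-carrier" as fixed effects. The only covariate whose effect may vary by visit is the baseline score: the list ends with "age at baseline, country, and baseline ADAS-Cog₁₃ total score-by-visit interaction". On the covariance, the section says "An unstructured variance-covariance matrix will be used".
- **Randomization.** Section 5.2.2: "The randomization will be stratified for disease status at baseline (MCI due to AD or mild AD", with allocation to the two doses "or placebo in a ratio of 1:1:1, stratified by MCI due to AD and mild AD dementia". No other stratification factor is named there or in Section 3.1.
- **Course of decline.** Section 12.3.1, comparing mild AD with MCI: "deterioration of cognition in patients with mild AD has been observed to be somewhat faster". It supports this with treatment differences and SDs. It gives no placebo decline for either stratum.

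**The concern.** A main effect on change from baseline forces the MCI versus mild AD gap to be the same at Week 13 as at Week 104. Faster decline in mild AD means that the gap grows. The model therefore does not match the protocol's own premise, and the mismatch is largest at the visit on which the primary contrast is taken. The stratification factor is in the model, but it does little work there. The stratum variation left unexplained at Week 104 goes into the residual variance, and so into the standard error used for the test and the confidence interval. The question is how much that costs.

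**Working it through.** **1. The plan's own power figure.** "The study will enroll a total of 2202 patients (734 patients per group"). "Assuming α =0.025 and the effect size among the patients who discontinue" have half the completers' effect, Section 12.3.1 states 96% power at an adjusted effect size of 0.21.

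Power ≈ Φ(d·√(n/2) − z), with z = 2.241 for two-sided 0.025:
- Overall: 0.21 × √367 = 4.023; Φ(4.023 − 2.241) = 96.3% (stated 96%).
- Mild AD, n = 0.65 × 734 ≈ 477, d = 0.24: 92.9% (stated 93%).
- MCI, n = 257, d = 0.14: 25.6% (stated 26%).

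The stated figures reproduce and do not depend on the missing term.

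**2. Inputs for the omitted interaction.**
- From the protocol: mix p = 0.65 mild AD (note to Table 7); Week 104 SDs 13.54 (mild AD) and 12.96 (MCI), Section 12.3.1; post-baseline ADAS-Cog13 visits at Weeks 13, 26, 52, 78 and 104 (Table 2).
- Pooled variance: 0.65 × 13.54² + 0.35 × 12.96² = 177.95, so SD = 13.34.
- Assumed, not in the protocol: the stratum gap D in points at Week 104, its linear growth, the SD at earlier visits, the within-patient correlations (autoregressive or exchangeable), and the correlation r of disease status with baseline score (0 to 0.5).
- Guide to D: the treatment differences differ by 3.83 − 2.24 = 1.59 points. If the drug slowed decline by the same fraction in both strata, D = 1.59 / fraction, that is 3.2 at 50% and 6.4 at 25%. The range used is 1 to 6.

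**3. What the constant effect captures.** Let g be the fitted constant stratum effect under generalized least squares. In the scenarios below, g lies between −0.13 and 0.09 points, so almost none of D is removed. Across other SD profiles that grow with time, g is about 0 to 30% of D. With a flat SD it is larger. For example, with first-order autoregressive correlation 0.8 the visit weights are 1, 0.2, 0.2, 0.2, 1 and the gap fractions are 0.125, 0.25, 0.5, 0.75, 1, so g/D = 1.425 / 2.6 = 55%. The table is therefore towards the upper end for a given D.

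**4. Inflation of the reported Week 104 variance.**

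Inflation = p(1−p)(1−r²)(D−g)² / 177.95, with p(1−p) = 0.2275. The factor 1−r² allows for what baseline score-by-visit already absorbs.

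Example, D = 6, r = 0, g = −0.13: 0.2275 × 6.13² / 177.95 = 4.8%; standard error √1.048 = 1.024.

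| D (points) | Variance inflation | SE inflation | Power with the term (96.26% without) |
|---|---|---|---|
| 1 | 0.09–0.13% | 0.05–0.07% | 96.27–96.28% |
| 2 | 0.37–0.53% | 0.19–0.27% | 96.32–96.35% |
| 4 | 1.5–2.1% | 0.7–1.1% | 96.50–96.59% |
| 6 | 3.3–4.8% | 1.7–2.4% | 96.77–96.97% |

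Top of the last row: 4.023 × 1.0237 = 4.118; Φ(4.118 − 2.241) = 97.0%. This counts the whole inflation as sampling variance, so it bounds the gain.

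**5. Is it real variance?** MMRMs were simulated with unstructured covariance, stratified allocation, about 27% dropout (more in mild AD), r = 0.5 and 150 runs per scenario. Each data set was fitted with and without the interaction. Variance ratios, without over with:

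| D | Model-based | Empirical |
|---|---|---|
| 2 | 1.004 | 1.005 |
| 4 | 1.016 | 1.002 |
| 6 | 1.034 | 0.997 |

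The two estimates correlate at 0.994 or more, and bias is under 0.02 points with either model. The estimator barely changes. Only its reported standard error does.

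**The case against.** The strongest defence is that the protocol's choice is coherent. Sections 3.3 and 6.2.1 treat MCI due to AD and mild AD as one continuum with overlapping score ranges and a boundary set by clinical judgment. Letting the continuous baseline score act differently at each visit models severity-dependent decline directly. That stands in part: at r = 0.5 the existing term absorbs r² = 25% of the stratum-by-visit variance and leaves the rest, and the protocol gives no value for r. It is also fair that power is already 96% and that a standard error erring on the large side does not threaten validity. Both points stand and set the low priority.

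Several stronger readings are tempting, but the documents do not support them:
- **Lost information.** A reader might convert a 2% variance figure into 0.02 × 2202 = 44 wasted patients. Stratified allocation already balances the arms on the omitted term, and the empirical variance ratios are 0.997 to 1.005, so no such information is lost.
- **A larger gap.** A reader might take D near 8 points; the fixed-fraction argument gives 1.59 / 0.20 = 7.95 at 20% slowing. The protocol states neither a slowing fraction nor a decline by stratum, and its wording suggests a modest difference.
- **Missing data.** A reader might infer that the omission weakens the missing-at-random adjustment if dropout differs by stratum. With assumed dropout of 35% in mild AD and 20% in MCI, equal across arms, the treatment estimate moved by at most 0.004 points. It moved by 0.07 to 0.14 only when dropout in mild AD was also assumed to differ by arm (45% versus 30%), and nothing in the protocol predicts that.
- **APOE4-by-visit.** A reader might extend the argument to APOE4. The protocol does not say that carriers decline faster, so the same ground is missing.

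**Conclusion.** The point holds as a small inefficiency in how the primary result is reported. The model omits an interaction that the protocol's own statement about decline implies, for the one factor used to stratify randomization. The consequence is a conservative model-based standard error, up to about 2.4% too large for an assumed Week 104 gap of up to 6 points, and a primary power gain of at most 0.7 percentage points. The treatment contrast is not biased, its true sampling variance hardly changes, and the sample size is unaffected.

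The size rests on assumptions that the protocol cannot settle: the gap itself, its linear growth, the SD and correlation over visits, and the overlap between disease status and baseline score. The direction does not depend on their exact values. A flatter SD profile or a stronger overlap makes the effect smaller still.

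**What to change.** Add disease status-by-visit to the primary ADAS-Cog13 MMRM in Section 12.2.4.1 and the synopsis, and fix it in the SAP, which Section 12.2.1 requires to be final before unblinding. Carry the same term into any secondary MMRM of the same form; Section 12.2.4.2 does not list those models' terms, so this is for consistency and does not correct a stated error.

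The cost is (5 − 1) × (2 − 1) = 4 degrees of freedom. Section 12.2.3 calls for separate test statistics for patients enrolled before and after the second interim analysis, so the term is estimated in each cohort. The smaller one is about 20% of 2202, or 440 patients, for whom four parameters are still a minor burden. No new data and no change to design or conduct are needed.

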The primary efficacy endpoint, change from baseline at Week 104 in ADAS-Cog₁₃ score, will be analyzed using a mixed-effect repeated-measures (MMRM) model that includes the fixed effects of treatment, visit (categorical covariate), treatment-by-visit interaction, disease status at baseline (MCI due to AD or mild AD), APOE4 status (carrier versus non-carrier), baseline ADAS-Cog₁₃ score (continuous covariate), concomitant acetylcholinesterase inhibitors (AChEI) use at baseline (yes/no), age at baseline, country, and baseline ADAS-Cog₁₃ score-by-visit interaction. Differences between treatment groups will be assessed using appropriate linear contrasts of the parameters in the MMRM model.

Secondary analyses

When a comparison between an AZD3293 dose group and the placebo group is statistically significant on the primary efficacy endpoint, the secondary efficacy endpoints for the AZD3293 dose group will be tested through a graphical approach which includes the primary efficacy endpoint. The order of testing and control of Type 1 error will be prespecified in the graphical analysis as stated in the SAP.

Exploratory efficacy variables will be analyzed using the MMRM models described above as well as with descriptive statistical analyses. These variables are listed above and in the SAP.

Biomarkers

Changes from screening in CSF biomarkers (eg, $A\beta_{1-42}$, total tau, and phosphorylated tau) will be analyzed using an MMRM analysis that includes the fixed effects of treatment, visit (categorical covariate), treatment-by-visit interaction, disease status at baseline (MCI due to AD versus mild AD), APOE4 status (carrier versus non-carrier), and predose biomarker value (continuous covariate).

Estimates of global cortical load from florbetapir F 18 amyloid PET and volumetric brain measures from MRI will be analyzed using the same methodology as described above for the CSF biomarker data.

Pharmacokinetics

Plasma and CSF AZD3293 and metabolite AZ13569724 concentrations will be summarized by treatment and time point using descriptive statistics.

A population PK analysis of plasma AZD3293 and AZ13569724 concentration data will be performed using a nonlinear mixed effects modelling approach. The results of the population PK analysis will be summarized in a separate report.

Pharmacokinetics-pharmacodynamics

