To control for the remote possibility that the study will be stopped for efficacy, a Haybittle-Peto adjustment (Haybittle 1971, Peto et al 1976) will be used if efficacy is tested at IA4. A significance level of α =0.001, will be used for treatment comparisons at the start of the multiplicity graph. The final analysis will use a significance level of α =0.05 for treatment comparisons between the AZD3293 treatment groups and the placebo group at the start of the multiplicity graph (see Section 12.2.3). Further details will be described in the interim analysis SAP.

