12.2.3. Multiplicity adjustments

The proposed study design contains several elements that require multiplicity adjustments to strongly control the family-wise error rate (FWER):

- Comparison of 2 AZD3293 treatment groups with the placebo group
- Changing the randomization ratio to 2:1 if a dose is dropped at the first or second interim analysis
- Sample size re-estimation at the second interim analysis

The first element, comparisons of the 2 AZD3293 treatment groups with the placebo group, is addressed by the use of a multiplicity graph. A graphical multiplicity strategy will be used for testing key secondary hypotheses to protect against Type I error of falsely rejecting a null hypothesis. The use of a prespecified analysis plan that employs Bretz' graphical approach will provide strong control of the study-wise Type I error rate for the primary and key secondary hypotheses at level α =0.05 (Bretz et al. 2009, 2011). The specific multiplicity graph will be detailed in the SAP.

In addition, to strongly control the FWER, a confirmatory adaptive design should satisfy the conditional invariance principle (Brannath et al 2007): separate test statistics will be calculated from the 2 patient cohorts (those patients enrolled prior to the second interim analysis [IA2], and those enrolled after IA2) and combined in a prespecified way (using the weighted inverse normal p-value combination method) for the final test decisions. Hence, any design modification that preserves the distributional properties of the separate test statistics under a given null hypothesis of interest will not lead to an inflation of the FWER. The p-value combination test principle combines the 2 p-values using a prespecified combination function and by construction satisfies the invariance principle. Details on the implementation of the measures to strongly control the FWER will be provided in the statistical analysis plan

A separate family of biomarkers will be tested at α =0.05. The family will include the biochemical biomarkers (CSF A β 1-42, total tau, and phosphorylated tau), as well as imaging biomarkers (amyloid PET and volumetric MRI).

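### Do Sections 12.2.3 and 12.2.4.1 set two incompatible decision rules for the primary endpoint?

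*Protocol*

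**What the plan says.** Section 12.2.4.1 gives the endpoint (change in ADAS-Cog13 at Week 104), two-sided hypotheses for each dose against placebo, the MMRM terms, an unstructured covariance matrix and the Week 104 least-squares-means difference. It then states: "This will be accomplished by using appropriate linear contrasts of the parameters in the model described above". The synopsis says the same more briefly: "Differences between treatment groups will be assessed using appropriate linear contrasts of the parameters in the MMRM model". Neither place mentions the IA2 cohorts.

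Section 12.2.3 lists sample-size re-estimation at IA2 among the features that need adjustment. For patients enrolled before and after IA2, "separate test statistics will be calculated from the 2 patient cohorts", and these are combined "using the weighted inverse normal p-value combination method) for the final test decisions". It adds: "The p-value combination test principle combines the 2 p-values using a prespecified combination function". It closes by handing over the mechanics: "Details on the implementation of the measures to strongly control the FWER will be provided in the statistical analysis plan".

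On levels, the interim-analysis section says: "The final analysis will use a significance level of α =0.05 for treatment comparisons between the AZD3293 treatment groups and the placebo group". That level is the one with which graphical testing begins. The power calculation in Section 12.3.1 works per dose: "Assuming α =0.025 and the effect size among the patients who discontinue without completing the study is 50% of the effect size".

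**The concern.** A reader who opens 12.2.4.1 alone sees one model, one contrast, no cohort term, no combination step and no pointer to 12.2.3. The natural picture is a single fit to everyone. Section 12.2.2.2 allows the total sample size to be raised at IA2 on unblinded efficacy data, with no stated maximum. A conventional pooled test after such an increase does not in general keep its nominal level. If 12.2.4.1 were the operative rule, the strong control claimed in 12.2.3 would not cover the primary result.

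Sidedness adds to the doubt. The hypotheses in 12.2.4.1 are two-sided, while 12.2.3 speaks of combining two p-values. Two-sided p-values carry no direction, so a cohort favouring placebo could reinforce a cohort favouring drug. At stake would be the validity of the primary p-value and some power.

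**Working it through.** **1. The passages side by side.**

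| Question | 12.2.3 | 12.2.4.1 and synopsis |
|---|---|---|
| Which endpoint, model and contrast? | Not addressed | MMRM, Week 104 difference |
| How are final decisions reached? | Cohort statistics, weighted inverse normal | Not addressed |
| One fit to all patients? | No: separate by cohort | Not stated |
| Sidedness of the combined p-values? | Not stated | Hypotheses two-sided; inputs not mentioned |

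A combination test needs a test statistic from each cohort, and the contrast in 12.2.4.1 is one. The two sections answer different questions and can both be followed.

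**2. The plan's own power figure.** Inputs from Section 12.3.1: 734 per group, adjusted effect size 0.21, α = 0.025 per dose. Taken as two-sided, the critical value is 2.2414.

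- Noncentrality: 0.21 × √(734/2) = 4.023.
- Power: Φ(4.023 − 2.2414) = 0.963, against 96% stated.
- With effect size 0.13 (ADCS-iADL): Φ(2.490 − 2.2414) = 0.598, against 60% stated.
- One-sided 0.025 would give 0.980 and 0.702, which do not match.

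**3. Do the two readings differ at the planned size?** IA2 falls at about 80% randomised, so the cohorts are about 0.8 × 734 = 587 and 147 per arm. Assume weights √0.8 and √0.2 (the protocol gives none). The combined statistic is √0.8·Z₁ + √0.2·Z₂. Under the normal approximation the pooled statistic weights Z₁ and Z₂ by the square roots of their shares of the sample, which are the same numbers. The correlation is 1.000 and power is 0.963 either way.

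**4. If the total rises to f times the plan (f assumed).** The correlation is √0.8·√(0.8/f) + √0.2·√((f − 0.8)/f). Combined power is Φ(4.023 × [0.8 + √0.2·√(f − 0.8)] − 2.2414). Pooled power is Φ(4.023·√f − 2.2414).

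| f | Correlation | Combined power | Pooled power |
|---|---|---|---|
| 1.10 | 0.996 | 0.975 | 0.976 |
| 1.25 | 0.984 | 0.986 | 0.988 |
| 1.50 | 0.959 | 0.994 | 0.996 |
| 2.00 | 0.912 | 0.998 | 0.9997 |

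**5. Error rate if a pooled test were used after an increase.** Nominal one-sided level per dose is 0.025/2 = 0.0125. The worst case picks, at every interim value, the sample size that maximises the conditional error. For a maximum total of 1.25 to 2 times the plan it gives:

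- interim information 0.2: 0.0132 to 0.0143
- interim information 0.5: 0.0138 to 0.0159
- interim information 0.8: 0.0148 to 0.0180

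The outcome depends on the rule. If the total goes to 1.5 times the plan only when conditional power is 50% to 90%, simulation gives 0.0118 (information 0.5) and 0.0110 (information 0.8) for the pooled test, both below 0.0125. The combination test simulates at 0.0126 to 0.0127, which is 0.0125 within simulation error. So it is not true that every change of sample size at IA2 breaks a pooled test, and the rule in 12.2.3 keeps its level in any case.

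**6. Sidedness.** Combining two-sided p-values with the same weights would cut power from 96% to 94% (effect size 0.21) and from 60% to 52% (effect size 0.13), and half of the null rejections would have cohorts pointing in opposite directions. No sentence prescribes this. A two-sided hypothesis is tested correctly by combining signed statistics, or one-sided p-values, and using both tails.

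**The case for a change.** The strongest reply is that the choice of statistic that decides the primary hypothesis is more than implementation, so deferring details to the SAP does not settle it. Section 12.2.4.2 opens secondary testing once the primary endpoint is significant, and a reader would look for that significance in 12.2.4.1. The synopsis describes the sample-size increase without mentioning the combination test. A pooled reading, if adopted, would exceed the nominal level under some rules, and a choice left open could be made after data are seen.

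Part of this stands. Neither 12.2.4.1 nor the synopsis points to 12.2.3, and one linking sentence would help. But the choice is not left open. Section 12.2.3 names the rule for the final decisions without conditions, and no other passage names a rival. Cohort-wise fitting, weights and sidedness are what a protocol commonly leaves to its SAP. Section 12.2.1 has the SAP finalised before unblinding, and Section 12.2.2.2 has the interim plan finalised before efficacy data are unblinded.

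**Conclusion.** There is no contradiction. Section 12.2.3 fixes how the decision is made and 12.2.4.1 fixes the model and contrast that feed it. Followed as written, the plan keeps its error control, and its stated power reproduces (0.963 against 96%).

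The inflation figures apply only to a pooled test that the protocol does not name as decisive, after an actual increase, under an adversarial rule. The losses from two-sided p-values apply to a procedure that the protocol does not specify. These calculations rest on assumptions outside the document: weights √0.8 and √0.2, the maximum sample size, the information at IA2, the re-estimation rule and a normal approximation. They cover the sample-size change, not a dropped dose. The verdict does not depend on them, because it follows from the wording of the two sections. The missing cross-reference is editorial.
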